visit, of $\geq 50\%$ of the Week 16 PASI improvement from baseline. That is, a patient will have relapsed during the Maintenance Period if their PASI score increases to at or above the midpoint between their baseline and Week 16 PASI score. **Rebound** is defined as having *one or more* of the following: worsening of psoriasis severity over baseline static Physician's Global Assessment (sPGA) score, worsening of psoriasis severity over baseline PASI score by 125%, or change in psoriasis phenotype (for example, from plaque to pustular) after randomization to placebo at Week 16.

Patients will be treated as follows:

- Patients who were responders to mirikizumab in the blinded Induction Period (responder definition is PASI 90 at Week 16) will be re-randomized 1:1:1 to 250 mg mirikizumab every 8 weeks (Q8W), 125 mg mirikizumab Q8W, or placebo Q8W, according to their randomized treatment assignment at Week 16 (see [Figure AMAK.1](#)). Stratification for the re-randomization will be based on body weight at baseline (< 100 kg or ≥ 100 kg).
 - Patients who relapse during the blinded Maintenance Period (see relapse criterion defined above) will remain on, or will be switched to, 250 mg mirikizumab for the remainder of the study and will be monitored for recapture of efficacy response. These patients will begin retreatment with mirikizumab at the visit at which relapse is identified and will receive another mirikizumab treatment at the next visit 4 weeks later. Subsequent mirikizumab treatments will be given at Q8W intervals.
- Patients who received placebo in the blinded Induction Period who are responders at Week 16 (Visit 7) will continue to receive placebo during the Maintenance Period until relapse; these patients will begin treatment with 250 mg mirikizumab at the visit at which relapse is identified and will receive another mirikizumab treatment at the next visit 4 weeks later. Subsequent mirikizumab treatments will be given at Q8W intervals.
- Patients who were not responders to mirikizumab in the blinded Induction Period will receive 250 mg mirikizumab Q8W.
 - Continued blinded treatment for nonresponders is provided so that partial or slow responders may remain in the study beyond Week 16, thus maintaining the study blind while patients continue to receive potentially beneficial longer-term treatment with mirikizumab.

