5.1. Determination of Sample Size

Approximately 500 patients will be randomized at a 4:1 ratio in the blinded Induction Period to receive 250 mg mirikizumab or placebo SC at Weeks 0, 4, 8, and 12. Stratified block randomization will be performed with the following stratification factors: previous exposure to biologic therapy (yes/no), body weight (<100 kg or ≥100 kg), and geographic region (North America or Other).

There are multiple primary endpoints in this study: static Physician’s Global Assessment (sPGA) (0,1) and PASI 90 at Week 16. The assumed sPGA (0,1) responses are 70% for the mirikizumab arm and 5% for the placebo arm. The assumed PASI 90 responses are 70% for the mirikizumab arm and 3% for the placebo arm. These assumptions are based upon the results of

the mirikizumab Phase 2 Study AMAF (Reich et al. 2017) and review of historical clinical studies in psoriasis (Langley et al. 2014; Gordon et al. 2016; Blauvelt et al. 2017; Papp et al. 2017; Reich et al. 2017).

With a total sample size of 500 patients, randomizing 400 patients to the mirikizumab arm and 100 patients to the placebo arm, this study has power of >95% for testing superiority of mirikizumab to placebo based on a 2-sided chi-square test with alpha of 5% on sPGA(0,1). It also provides a power of >95% for testing superiority of mirikizumab to placebo on PASI 90 based on a 2-sided chi-square test with alpha of 5%.

In order to account for multiple testing for the comparisons of 2 mirikizumab groups against the placebo group in the Maintenance Period, a 2-sided chi-square test at the 0.025 level is assumed. Assuming 70% of the mirikizumab patients are re-randomized in the Maintenance Period at Week 16 (Visit 7) at a 1:1:1 ratio to 250 mg mirikizumab Q8W, 125 mg mirikizumab Q8W or placebo, approximately 93 patients will be included in each treatment group. Stratified block randomization will be performed with the stratification factor of body weight at baseline (<100 kg or \geq 100 kg). This sample size will provide >95% power to test the difference in the proportion of patients maintaining PASI 90 from Week 16 (Visit 7) after re-randomization at the start of the Maintenance Dosing Period to Week 52 (Visit 16) between each mirikizumab dosing interval and placebo, assuming the proportions of patients maintaining PASI 90 are 80% for 250 mg mirikizumab Q8W, 70% for 125 mg mirikizumab Q8W, and 10% for placebo.

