Induction Safety	All randomized patients who received at least 1 dose of study treatment . Safety analyses for the induction period will be conducted on this population.
Re-randomized Maintenance ITT	All Induction ITT patients who received at least 1 induction dose of study treatment and have been re-randomized at Week 16. Efficacy and health outcomes analyses for the maintenance period will be conducted on this population.
Re-randomized Maintenance Safety	All Induction ITT patients who received at least 1 induction dose of study treatment, have been re-randomized at Week 16 and have received at least 1 maintenance dose . Safety analyses for the maintenance period will be conducted on this population.
Non-re-randomized Maintenance ITT	All Induction ITT patients who received at least 1 induction dose of study treatment, have not been re-randomized at Week 16, and have entered the maintenance period (Table AMAK.6.3). Efficacy analyses for the maintenance period will be conducted on this population.
Maintenance ITT	Pooled re-randomized and Non-re-randomized populations.
Re-randomized Relapsed	All Re-randomized Maintenance ITT patients who relapse during the Maintenance Period and received a 250-mg dose. These patients will be analyzed for recapture of efficacy response.
All Miri Safety	All randomized patients who received at least 1 dose of mirikizumab . Patients who received placebo for the entire study are not included.
Induction PPS	All randomized patients who do not have important protocol deviations excluded from per protocol analysis (IPDPP) in the induction period. IPDPP are described in a separate document: “The AMAK Trial Issues Management Plan.” These patients will be used as a sensitivity analysis for the primary endpoints only.

Abbreviations: ETV = early termination visit; ITT = intent-to-treat; PPS = per protocol set.

Table AMAK.6.2. Treatment Groups and Comparisons for Each Study Period and Analysis Population

Study Period	Analysis Population	Treatment Groups	Inferential Comparisons
Induction	Induction ITT Induction Safety Induction PPS	placebo Q4W; 250 miri Q4W	250 miri Q4W vs. placebo Q4W
Maintenance	Re-randomized Maintenance ITT; Re-randomized Maintenance Safety	placebo Q8W ^e ; 125 miri Q8W; 250 miri Q8W; Total miri*	125 miri Q8W vs. placebo Q8W; 250 miri Q8W vs. placebo Q8W
	Re-randomized Relapsed	placebo Q8W ^a e; 125 miri Q8W ^a ; 250 miri Q8W ^a ; Total miri*	No comparison

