	Non-re-randomized Maintenance	miri nonresponder ^b ; placebo nonresponder ^c placebo responder ^d	No comparison
	Maintenance ITT	placebo Q8W ^e ; 125 miri Q8W; 250 miri Q8W; miri nonresponder ^b ; placebo responder ^d placebo nonresponder ^c ;	No comparison
All	All Miri Safety	all miri ^f ; all miri + placebo withdrawal ^e ^f ; all miri + placebo withdrawal ^e + FUP ^f	No comparison

Abbreviations: FUP = follow-up; ITT = intent-to-treat; miri = mirikizumab; PASI 90 = $\geq 90\%$ improvement from baseline in the Psoriasis Area and Severity Index; PPS = per protocol set; Q4W = administration once every 4 weeks; Q8W = administration once every 8 weeks; vs. = versus.

* For safety related analysis only.

^a Treatment is the treatment patient was receiving immediately before relapse.

^b Patients randomized to mirikizumab in induction who do not achieve PASI 90 at Week 16 receive 250 mg Q8W.

^c Patients randomized to placebo in induction who do not achieve PASI 90 at Week 16 receive 250 mg Q8W.

^d Patients randomized to placebo in induction who achieve PASI 90 at Week 16 continue to receive placebo.

^e Patients re-randomized to Placebo in Maintenance Period.

^f Technically, there is only 1 treatment group. However, all summaries utilizing the “All Miri Safety” will include a summary for different periods:

- all miri: only the period of exposure to miri treatment.
- all miri + placebo withdrawal: period of exposure to miri treatment + placebo withdrawal.
- all miri + placebo withdrawal + FUP: period of exposure to miri treatment + placebo withdrawal + follow up.

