6.1.2. Study Time Intervals

Table AMAK.6.3 displays a list of study periods along with the definition of which patients will be considered to have entered the study period and when the individuals start and end the study period. The table shows both a date and a time.

To calculate the length of any time interval or time period in this study, the following formula will be used:

$$\text{Length of interval (days)} = \text{End Date} - \text{Interval Start Date} + 1$$

To convert any time length from days to years, the following formula will be used:

$$\text{Length of interval (years)} = \text{Length of interval (days)} / 365.25$$

To convert any time length from days to weeks, the following formula will be used:

$$\text{Length of interval (weeks)} = \text{Length of interval (days)} / 7$$

Only for the purpose of calculating the length of study period time intervals, the words “prior to” in [Table AMAK.6.3](#) should be understood to mean “the day before,” while the word “after” should be understood to mean “the day after.”

Table AMAK.6.3. Definition of Study Period Time Intervals

Study Period	Start Definition	End Definition
Screening: All patients who sign informed consent are considered as entering the Screening Period.	Informed consent date	Prior to the start of induction.
Induction Period Interval: All patients who are randomized to the study are considered as entering the Induction Period.	At the first injection date/time ^a following randomization. For patients who are randomized but not dosed, the Induction Period starts on the date of randomization.	Prior to the start of maintenance. For patients who discontinue before or on the Week 16 visit, the induction period ends at the last date of treatment discontinued date or last treatment visit date.
Maintenance Period Interval: All patients who had any Week 16 to Week 52 visits (except the ones who discontinued the study at Week 16) are considered to have entered the Maintenance Period.	At the Week 16 dosing date/time ^a . If a patient is unable to be dosed at the Week 16 visit, the Maintenance Period starts at the Week 16 visit. If the patient misses the Week 16 visit, the Maintenance Period starts at Day 118.	After the Week 52 visit date. If patients discontinued prior to Week 52, the Maintenance Period ends at the last date of treatment disposition date or last treatment visit date. If the patient relapsed, the Maintenance Period ends before the patient entered the relapse period.

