6.13. Safety Analyses

[figure not shown]
The planned analyses of safety data will be performed with an intent to maintain consistency with compound level safety standards. These standards are based on internal standards which were informed by Clinical Data Interchange Standards Consortium (CDISC) standards, regulatory guidance (e.g., Food and Drug Administration [FDA] Clinical Review Template), and cross-industry standardization efforts (e.g., Pharmaceutical Users Software Exchange [PhUSE] white papers from the Standard Analyses and Code Sharing Working Group provided in the PhUSE Computational Science Deliverables Catalog [WWW]).

All safety evaluations will be based upon the following safety analysis populations with their associated study periods:

- Induction Safety Population
- Re-randomized Maintenance Safety Population
- All Miri Safety Population

These analysis populations are fully defined in [Table AMAK.6.1](#), while [Table AMAK.6.2](#) describes the treatment groups, associated study periods and the comparisons for each analysis

population. Figure AMAK.6.2 gives a graphical depiction of each of the 3 safety populations along with the treatment groups, associated study periods and the comparisons for each analysis population.

Abbreviations: LV = last study visit; miri = mirikizumab; Q4W = administration once every 4 weeks; Q8W = administration once every 8 weeks; V = visit; w = weeks; W = week.

* Option to enter Study AMAH or to enter the Post-Treatment Follow-Up Period.

a Patients may receive placebo injections during the Maintenance Period to maintain the study blind across treatment groups.

b Patients who relapse during the Maintenance Period will be treated with 250 mg mirikizumab for the remainder of the study and will be monitored for recapture of efficacy response,

c First Maintenance Period dosing at Week 16.

Figure AMAK.6.2. Illustration of safety populations within the study design.

Unless otherwise noted, Fisher’s exact test will primarily be used to compare percentages, and odds ratios will be provided. Odds ratios will be created with mirikizumab treatment as the numerator and placebo as the denominator.

Treatment differences in mean change for continuous measurements will be assessed using an analysis of covariance (ANCOVA) model containing terms for treatment and the continuous covariate of baseline measurement. Type 3 sums of squares will be used. The significance of

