6.13.1. Extent of Exposure

Duration of exposure to study treatment will be summarized by treatment group for each of the three safety analysis populations (i.e., Induction Safety, Re-randomized Maintenance Safety, and All Miri Safety). For the treatment period of interest associated with each safety analysis population, exposure will be calculated as the time period length in years (see Section 6.1.2) with start and end dates described in Table AMAK.6.3. The following periods will be used for calculations:

- For the Induction Safety Population, the Induction Period Interval will be used.
- For the Re-randomized Maintenance Safety Population, the Maintenance Period Interval will be used. As noted in Table AMAK.6.3, patients who relapse after re-randomization during the maintenance period are considered to have left the maintenance period and entered the relapse period.
- For the All Miri Safety Population, we calculate the exposure for 3 different period definitions:
 - Exposure for “all miri” will be calculated by finding the length of the “All Miri Period.” For patients who are re-randomized to placebo, the “All Miri Period” may be composed of two non-overlapping periods of time, and the length of the two periods of time will be summed.
 - Exposure for “all miri + placebo withdrawal” will be calculated as the length of the “All Miri + Placebo Withdrawal Period.”
 - Exposure for “all miri + placebo withdrawal + follow-up (FUP)” will be calculated as the length of the “All Miri + placebo withdrawal + FUP Period.”

Total patient-years (PY) of exposure will be reported for each of the three safety analysis populations by treatment group (see Table AMAK.6.2). Descriptive statistics will be provided for patient-weeks of exposure and the frequency of patients falling into different exposure ranges will be summarized:

- >0; ≥4 weeks; ≥8 weeks; ≥12 weeks; ≥16 weeks; ≥24 weeks; ≥32 weeks; ≥40 weeks; and ≥48 weeks
- >0 to <4 weeks; ≥4 weeks to <8 weeks; ≥8 weeks to <12 weeks; ≥12 weeks to <16; ...; ≥48 weeks

Additional exposure ranges may be considered, if necessary. No p-values will be reported in these tables as they are intended to describe the study populations, rather than test hypotheses about them.

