6.13.2. Adverse Events

A treatment-emergent adverse event (TEAE) is defined as an event that first occurred or worsened in severity after baseline. The MedDRA Lowest Level Term (LLT) will be used in the treatment-emergent computation. The maximum severity for each LLT during the baseline period will be used as baseline. The treatment period will be included as postbaseline for the analysis. For events with a missing severity during the baseline period, it will be treated as “mild” in severity for determining treatment-emergence. Events with a missing severity during the postbaseline period will be treated as “severe” and treatment-emergence will be determined by comparing to baseline severity. For events occurring on the day of first taking study medication, the start times of the study treatment and AE will be used to determine whether the event was pre- versus post-treatment. If start time for the AE is missing, it will be assumed to have started in the later period.

Summary tables as described in [Table AMAK.6.7](#) will be presented for the three safety populations/ periods, as indicated. Summary tables will include the number and percentage of patients reporting an event. For events that are gender-specific (as defined by MedDRA), the number of participants at risk will include only patients from the given gender. Comparisons will be performed using Fisher’s exact test. P-values should be interpreted cautiously due to the fact that multiplicity is not controlled.

For the three safety populations, the baseline period and postbaseline periods (see [Figure AMAK.6.2](#)) will be defined as follows:

- *Induction Safety Population*: The baseline period is the Screening Period. The postbaseline period will be the Induction Period.
- *Re-randomized Maintenance Safety Population*: The baseline events are those events which are ongoing at the start of the Maintenance Period (i.e., the baseline period is a moment in time). The postbaseline period is defined as the Maintenance period.
- *All Miri Safety Population*: The baseline period for patients randomized to mirikizumab during induction is the screening period. For all other patients, the baseline events are those events which are ongoing at the time of first injection with mirikizumab. Three different postbaseline periods will be used:

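### Maintenance AE comparisons use crude percentages and odds ratios over a window that closes at relapse, so a shorter placebo window biases them against mirikizumab

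*SAP*

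**What the plan says.** - **Comparison.** SAP Table AMAK.6.2 lists, for the Re-randomized Maintenance Safety population, the inferential comparisons "125 miri Q8W vs. placebo Q8W; 250 miri Q8W vs. placebo Q8W".
- **Measure.** SAP 6.13.2: "Summary tables will include the number and percentage of patients reporting an event". The test is Fisher's exact test. SAP 6.13 adds odds ratios: "Odds ratios will be created with mirikizumab treatment as the numerator and placebo as the denominator". A value above 1 therefore counts against mirikizumab.
- **Window.** For this population the postbaseline period in SAP 6.13.2 is the Maintenance Period. Table AMAK.6.3 closes it early for some patients: "If the patient relapsed, the Maintenance Period ends before the patient entered the relapse period". SAP 6.13.1 repeats the rule for exposure: "patients who relapse after re-randomization during the maintenance period are considered to have left the maintenance period and entered the relapse period".
- **After relapse.** Follow-up continues. Under Protocol 5.1.3, relapsed patients "will remain on, or will be switched to, 250 mg mirikizumab for the remainder of the study". Their later events enter the All Miri Safety summaries, which have no comparator; the footnote to Table AMAK.6.2 says "Technically, there is only 1 treatment group".
- **Exposure.** SAP 6.13.1 reports total patient-years by treatment group. The SAP text specifies no event rate per patient-year and no time-to-first-event analysis for AEs.
- **Protocol.** Section 10.3.4 names a comparison with placebo for Induction safety, but only a summary by treatment for Maintenance.

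**The concern.** Closing the AE window when the patient switches to 250 mg is a defensible on-treatment choice. The difficulty is the denominator: a crude percentage treats a patient observed for 8 weeks like one observed for 36.

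The design makes the windows unequal. SAP 5.1 assumes that PASI 90 is maintained in "80% for 250 mg mirikizumab Q8W, 70% for 125 mg mirikizumab Q8W, and 10% for placebo". Loss of PASI 90 is not relapse, so these figures show the expected direction only. The better the drug prevents relapse, the longer its AE window and the higher its crude AE percentage.

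A reader of the maintenance tables could then see an excess of AEs on mirikizumab that reflects observation time alone. The SAP's caution about p-values refers to uncontrolled multiplicity, not to unequal follow-up.

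**Working it through.** **The plan's own figures.** The number per arm is 400 × 0.70 / 3 = 93.3, so about 93. For maintained PASI 90 at two-sided alpha 0.025, a pooled chi-square calculation with 93 per arm gives power above 99.9% for both 80% vs 10% and 70% vs 10%. This agrees with the stated >95%. The documents state no operating figure for the safety comparison.

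**Inputs from the documents.** 93 per arm; a full window of 36 weeks (Week 16 to 52); visits every 4 weeks; Fisher's exact test, two-sided, at 0.05.

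**Assumptions (not in the documents).** The same constant AE hazard in every arm, so no true effect. Relapse visits spread evenly over Weeks 20 to 48. Placebo relapse 40%, 60% or 80%; mirikizumab relapse 5%, 20% or 30%.

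**Formulas.** With R the AE risk over 36 weeks and r the relapse proportion:

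- h = −ln(1 − R)/36 per week
- t = relapse visit week − 16
- mean window = r × mean(t) + (1 − r) × 36
- P(event) = r × mean(1 − e^(−ht)) + (1 − r) × (1 − e^(−36h))

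**One case in full: R = 50%, placebo relapse 60%, mirikizumab relapse 20%.**

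- h = 0.6931/36 = 0.01925. t runs from 4 to 32 with mean 18, and mean(1 − e^(−ht)) = 0.2818.
- Placebo: window 0.6 × 18 + 0.4 × 36 = 25.2 weeks; P = 0.6 × 0.2818 + 0.4 × 0.5 = 0.369.
- Mirikizumab: window 0.2 × 18 + 0.8 × 36 = 32.4 weeks; P = 0.2 × 0.2818 + 0.8 × 0.5 = 0.456.
- Odds ratio = 0.839/0.585 = 1.43, with no true effect.
- Summing over all pairs of Binomial(93) outcomes, Fisher's test gives p<0.05 with the excess on mirikizumab in 17.7% of trials. With equal windows it does so in 1.7%.

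**Range at 50% AE risk.** Mean placebo windows are 28.8, 25.2 and 21.6 weeks at 40%, 60% and 80% placebo relapse.

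| Mirikizumab relapse (mean window) | Null odds ratio at placebo relapse 40 / 60 / 80% | False flags against mirikizumab |
|---|---|---|
| 5% (35.1 weeks) | 1.36 / 1.64 / 1.98 | 14 / 32 / 56% |
| 20% (32.4 weeks) | 1.19 / 1.43 / 1.74 | 6 / 18 / 39% |
| 30% (30.6 weeks) | 1.09 / 1.31 / 1.59 | 3 / 11 / 28% |

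**Other settings.**

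- At 30% AE risk, false flags are 9/18/33%, 5/11/22% and 3/7/16% for the same three rows.
- With relapse only from Week 28 and 50% AE risk, they are 4.5/10.5/21% at 20% mirikizumab relapse and 2.8/7.0/15% at 30%.
- For rarer events (Weeks 20–48, 5% mirikizumab relapse), they are 3.5–9.6% at 10% AE risk, 1.8–3.7% at 5% and 0.2–0.3% at 2%. The odds ratio is still 1.22–1.67.
- If all AE risk falls before the first relapse, the bias is zero.

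**A different relapse model.** With exponential relapse from Week 16 and 20% AE risk, placebo/mirikizumab relapse of 30/5%, 50/5% and 70/10% gives odds ratios of 1.19, 1.42 and 1.74. With no relapse in the first 12 weeks these fall to 1.12, 1.24 and 1.39. SAP 6.3.1 counts relapsers as non-responders, so the design figures cap relapse at 90% on placebo and 20% on 250 mg. At that ceiling the odds ratio is 2.48, or 1.64 with the 12-week lag. The direction is the same whenever placebo relapses more.

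**The alternative measure.** In 20,000 simulated trials per scenario (first model), the ratio of first events per patient-year at risk averaged 1.00–1.01 at 30–50% AE risk and 1.00–1.05 at 10%. It flagged mirikizumab in 2.0–2.6% and 0.9–1.8% of trials respectively.

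**The case against.** The strongest reply has four parts.

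1. **Exposure-adjusted rates may already be planned.** SAP 6.13 aligns the safety analyses with compound level safety standards, and SAP 6.13.8 defers the types of AESI summaries to them. Those standards were not available. This stands as a limit: the point concerns the SAP text. But 6.13.2 itself specifies percentages and Fisher's test and cites no rate.
2. **The imbalance is visible.** Patient-years, patient-weeks and exposure ranges are reported by arm, and 6.13.1 says that relapsers leave the period. A reader can see unequal follow-up, but the odds ratios and p-values remain uncorrected.
3. **The consequence is limited and the size is assumed.** These tests lie outside the controlled family, and a bias in this direction does not hide a harm of mirikizumab. Relapse is a stricter event than loss of PASI 90. The largest figures need 80% placebo relapse, 5% mirikizumab relapse and relapses from Week 20. In a mild case (40% vs 20% relapse, from Week 28, 30% AE risk) the odds ratio is 1.11 and false flags are 3.6%. Many table rows are single preferred terms or SAEs, where Fisher's test seldom rejects. All of this stands, and it keeps the point at the level of a recommended change.
4. **Fisher's test is the protocol default, and the rate check is favourable by construction.** Protocol 10.3.1 does set Fisher's test for categorical safety data, but with an exception where otherwise specified. Section 10.3.4 asks only for a summary in Maintenance and can be read as that exception. The simulation does assume a constant hazard and relapse unrelated to AE risk, the conditions under which rates are unbiased. It shows that rates remove the window effect, not that they remove every bias.

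**Conclusion.** The concern holds. Followed as written, the SAP gives crude maintenance AE percentages and odds ratios that are biased against mirikizumab whenever placebo patients relapse more and some AE risk falls after relapses begin. With 20–30% relapse on mirikizumab, 40–80% on placebo and 50% AE risk, the null odds ratio is 1.09–1.74 and false flags occur in 3–39% of trials, against 1.7% with equal windows. For common outcomes such as any TEAE, false significance is a real possibility. For single terms and SAEs the main problem is a biased estimate. The mechanism and direction follow from the SAP text and the design. The size rests on assumed relapse and AE rates and on a constant, equal AE hazard. No primary or major secondary conclusion is affected; the change is advisable, not essential.

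**What to change.** For the Re-randomized Maintenance Safety population:

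- Base the between-arm AE comparison on exposure-adjusted incidence rates: patients with an event per 100 patient-years at risk, censored at first event or period end, with a rate ratio or difference and 95% CI.
- Keep crude percentages as description, without Fisher p-values. This matches Protocol 10.3.4.
- As a check, add Kaplan-Meier cumulative incidence for any TEAE and the main AESIs, or a crude comparison over a common early window fixed before the Week 52 database lock.
- If the compound level safety standards already define such rates, cite them in SAP 6.13.2.

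The cost is SAP wording, a few table columns and a derivation of time to first event. Period lengths and total patient-years are already planned. The downside is that rates assume a roughly constant hazard, and neither rates nor Kaplan-Meier estimates remove informative censoring at relapse.
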